8.2.2 SPLEEN AND LIVER

Both the spleen and liver will be assessed by CT/MRI scan and by physical examination on deep inspiration at baseline and as per the study assessment schedule. The baseline and nadir values for the longest vertical dimension (LVD) of each organ will be used as reference to further characterize the objective tumor response of the measurable dimensions of the CLL during treatment. All spleen and liver LVD measurements should be recorded in centimeters.

8.2.3 NON-TARGET LESIONS

Any other measurable and abnormal nodal lesions not selected for quantitation as target lesions may be considered non-target lesions. In addition, non-measurable evidence of CLL such as nodal lesions with both diameters $< 1.0 \text{ cm}$, extra-nodal lesions, bone lesions, leptomeningeal disease, ascites, pleural or pericardial effusions, lymphangitis of the skin or lung, abdominal masses that are not confirmed and followed by imaging techniques, cystic lesions, previously irradiated lesions, and lesions with artifacts may be considered as non-target disease.

The presence or absence of non-target disease should be recorded at baseline and at the stipulated intervals during treatment. If present at baseline, up to 6 non-target lesions should be recorded. The non-target disease at baseline will be used as a general reference to further characterize regression or

progression of CLL during assessments of the objective tumor response during treatment. Measurements are not required and these lesions should be followed as “present” or “absent”.

8.3 DEFINITIONS OF TUMOR RESPONSE AND PROGRESSION

Responses will be categorized by the IRC as CR, CRI, PR, PR-L, SD, or PD. In addition, a response category of not evaluable (NE) is provided for situations in which there is inadequate information to otherwise categorize response status.

The best overall response will be determined. The best overall response is the best response recorded from the start of treatment until disease/recurrence progression (taking as a reference for disease progression the smallest measurements recorded since treatment started). Where imaging data are available, these data will supersede physical examination data in determining tumor status.

8.4 COMPLETE RESPONSE

To satisfy criteria for a CR, all of the following criteria must be met:

- No evidence of new disease
- ALC in peripheral blood of $<4 \times 10^9/L$
- Regression of all target nodal masses to normal size ≤ 1.5 cm in the LD
- Normal spleen and liver size
- Regression to normal of all nodal non-target disease and disappearance of all detectable non-nodal, non-target disease
- Morphologically negative bone marrow defined as $<30\%$ of nucleated cells being lymphoid cells and no lymphoid nodules in a bone marrow sample (the presence of benign reactive nodules is still compatible with a CR)
- Absence of constitutional symptoms
- Peripheral blood counts meeting all of the following criteria:
 - ANC $>1.5 \times 10^9/L$ without need for exogenous growth factors (e.g., G-CSF)
 - Platelet count $\geq 100 \times 10^9/L$ without need for exogenous growth factors
 - Hemoglobin $\geq 110 \text{ g/L}$ (11.0 g/dL) without red blood cell transfusions or need for exogenous growth factors (e.g., erythropoietin)

Patients who fulfill all the criteria for a CR (including bone marrow criteria) but who have a persistent anemia, thrombocytopenia, or neutropenia or a hypocellular bone marrow that is related to prior or ongoing drug toxicity (and not to progressive CLL) will be considered as a CR with incomplete marrow recovery (CRI). These patients remain eligible for MRD assessments and will discontinue therapy if negative for residual disease (similar to management for patient achieving a CR)

8.5 PARTIAL RESPONSE

To satisfy criteria for a PR, all of the following criteria must be met:

- No evidence of new disease
- Change in disease status meeting ≥ 2 of the following criteria, with 2 exceptions in which only 1 criterion is needed: 1) only lymphadenopathy is present at baseline; 2) only lymphadenopathy

Acalabrutinib + low dose SQ Rituximab

Dated: 06OCT2022

Page 38 of 59

and lymphocytosis are present at baseline. In these 2 cases, only lymphadenopathy must improve to the extent specified below:

- In a patient with baseline lymphocytosis (ALC $\geq 4 \times 10^9/L$), a decrease in peripheral blood ALC by $\geq 50\%$ from baseline or a decrease to $< 4 \times 10^9/L$
- A decrease by $\geq 50\%$ from the baseline in the SPD of the target nodal lesions
- In a patient with enlargement of the liver or spleen at baseline, a decrease by $\geq 50\%$ from baseline
- A decrease by $\geq 50\%$ from baseline in the CLL marrow infiltrate or in B-lymphoid nodules
- No target, splenic, liver, or non-target disease with worsening that meets the criteria for definitive PD
- Peripheral blood counts meeting 1 of the following criteria:
 - ANC $> 1.5 \times 10^9/L$ or $> 50\%$ increase over baseline without need for exogenous growth factors (e.g., G-CSF)
 - Platelet count $> 100 \times 10^9/L$ or $\geq 50\%$ increase over baseline without need for exogenous growth factors
 - Hemoglobin $> 110 \text{ g/L}$ (11.0 g/dL) or $\geq 50\%$ increase over baseline without red blood cell transfusions or need for exogenous growth factors (e.g., erythropoietin)

PR criteria met but without recovery of lymphocytosis = PR-L

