3.1 INCLUSION CRITERIA

Patients must meet all of the following inclusion criteria to be eligible for participation in this study:

1. Diagnosis of B-cell CLL or SLL, with diagnosis established according to IWCLL criteria and documented within medical records. Patients must not have received previous therapy for CLL/SLL
2. CLL/SLL that warrants treatment consistent with accepted IWCLL criteria for initiation of therapy. Any one of the following conditions constitutes CLL/SLL that warrants treatment:
 - a. Evidence of progressive marrow failure as manifested by the onset or worsening of anemia and/or thrombocytopenia, or
 - b. Massive (i.e., lower edge of spleen \geq 6 cm below the left costal margin), progressive, or symptomatic splenomegaly, or
 - c. Massive (i.e., \geq 10 cm in the longest diameter), progressive, or symptomatic lymphadenopathy, or
 - d. Progressive lymphocytosis in the absence of infection, with an increase in blood absolute lymphocyte count (ALC) \geq 50% over a 2-month period or lymphocyte doubling time of <6 months (as long as initial ALC was \geq 30,000/L), or
 - e. Autoimmune anemia and/or thrombocytopenia that is poorly responsive to corticosteroids or other standard therapy, or
 - f. Constitutional symptoms, defined as any one or more of the following disease-related symptoms or signs occurring in the absence of evidence of infection:
 - i. Unintentional weight loss of \geq 10% within the previous 6 months, or
 - ii. Significant fatigue (\geq Grade 2), or
 - iii. Fevers $>100.5^{\circ}\text{F}$ or 38.0°C for \geq 2 weeks, or
 - iv. Drenching night sweats for >1 month.
3. Adequate organ system function, defined as follows:
 - a. Absolute neutrophil count (ANC) \geq $0.5 \times 10^9/\text{L}$ and platelet count \geq $30 \times 10^9/\text{L}$
 - b. Total bilirubin \leq 2.5 times the upper limit of normal (ULN) unless due to Gilbert's disease
 - c. Alanine aminotransferase (ALT) and aspartate aminotransferase (AST) \leq 2.5 x ULN if no liver involvement or \leq 5 x the ULN if known liver involvement
 - d. Calculated creatinine clearance >30 mL/min (as calculated by the Cockcroft-Gault formula)
 - e. Patients with PT/INR or aPTT \leq 2xULN.
4. ECOG performance status \leq 2 unless related to CLL.
5. Male or female \geq 18 years of age.
6. Ability to swallow and retain oral medication.

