4 STUDY DESIGN

4.1 OVERVIEW OF STUDY DESIGN

This is an open label, Phase II trial of acalabrutinib and high frequency low dose subcutaneous rituximab in previously untreated CLL patients requiring therapy. Subjects will be recruited from the James P. Wilmot Cancer Center, University of Rochester in Rochester, New York. Patients seen in the inpatient or outpatient setting with histologically confirmed untreated CLL will be evaluated for this study.

Patients will be treated with the following combination:

Rituximab: day 1 = 50 mg IV, then 50 mg SQ 2 x weekly for 6 cycles. Note that in the event of a first dose infusion reaction, subsequent doses may be given IV if felt necessary by the treating investigator.

Acalabrutinib: 100 mg po BID starting on day 8 of cycle 1. First dose prior to rituximab on day 8.

- Response assessments will be performed prior to the completion of cycle 12. Patients who have attained a radiographic complete response will undergo a BM biopsy to confirm CR. Patients in CR will also have MRD testing performed on peripheral blood and marrow. Patients in CR and undetectable for MRD, will stop therapy and be followed until disease progression.
- Patients not in a MRD negative CR, will continue acalabrutinib.
- Repeat response assessments will be performed at 24 cycles of therapy for those continuing on acalabrutinib. Patients in CR and undetectable for MRD, will stop therapy and be followed until disease progression, unacceptable toxicity or physician/patient discretion.

All cycles will be 28 days.

Patients will be followed until the occurrence of definitive disease progression and may discontinue therapy early for unacceptable toxicity or withdrawal from the study due to investigator decision or other reasons.

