⁶ Baseline CT scan within 60 days prior to Cycle 1/Day 1. CT Scan/Response Assessment +/- 7 day window. CT Scan/Response assessment end of cycle 12 and at the end of cycle 24 for patients continuing on acalabrutinib. Follow up CTs to be done at investigator discretion/ per standard of care. CTs at cycle 12 and 24 will not be required if a patient does not have measurable disease at baseline.

⁷ Visits every 3 months (+/- 1 month) or as per investigator discretion. Treatment Administration and labs or other assessments +/- 7 day window from visit.

⁸ Serum or urine pregnancy test prior to Cycle 1 / Day 1 and within 30 days following discontinuation for females of childbearing potential. If patient has experienced menopause or no longer has uterus / ovaries this can be omitted.

⁹ Bone Marrow sample performed prior to completion of cycle 12 and/or cycle 24 to confirm a complete response / MRD negativity

¹⁰ Flow cytometry of peripheral blood for minimal residual disease assessment is being performed prior to completion of cycle 12 and at cycle 24 for patients continuing on acalabrutinib. A patient in CR will undergo a bone marrow biopsy to confirm the response. Bone marrow and peripheral blood samples will be analyzed and stored in the laboratory of [name] at the University of Rochester.

¹¹ Follow-up for SAEs should continue until resolution, stabilization, the subject has withdrawn consent or has been lost to follow-up.

¹² Patients not in a MRD negative complete remission will continue acalabrutinib.

¹³ Acalabrutinib is dosed twice daily every day, unless treatment is held or discontinued, starting Cycle 1 Day 8.

¹⁴ At a minimum, hematology includes white blood cells and differential, hemoglobin, hematocrit, mean corpuscular volume, platelets.

¹⁵ At a minimum, chemistry includes sodium, potassium, chloride, bicarbonate, urea nitrogen, creatinine, glucose, calcium, phosphorus, albumin

¹⁶ Chemistry, uric acid and LDH will be repeated 6-8 hours after treatment initiation and as further clinically indicated for patients with a high tumor burden, which is defined as having any lymph nodes >10cm or lymph nodes >5cm with an absolute lymphocyte count>25 x10⁹/L

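### Section 8.5 leaves patients with only lymphocytosis, or only liver or spleen enlargement, at baseline with one scorable PR criterion where two are needed

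*Combined protocol and SAP*

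**What the plan says.** Section 8.5 lists four disease changes that can count towards PR: lymphocyte count, summed product of the target nodes, liver or spleen enlargement, and marrow. At least two must be met, "with 2 exceptions in which only 1 criterion is needed". The first exception is that "only lymphadenopathy is present at baseline". The second is lymphadenopathy "and lymphocytosis are present at baseline. In these 2 cases, only lymphadenopathy must improve to the extent specified below". The marrow change is measured "from baseline in the CLL marrow infiltrate or in B-lymphoid nodules". Blood counts and absence of worsening are separate conditions and do not count towards the two.

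Table 5.1 shows no marrow in the screening column. Footnote 9 describes the sampling as "Bone Marrow sample performed prior to completion of cycle 12 and/or cycle 24 to confirm a complete response / MRD negativity", and section 4.1 says who is sampled: "Patients who have attained a radiographic complete response will undergo a BM biopsy to confirm CR".

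Under section 3.1, item 2, any one treatment indication is enough for entry, and progressive lymphocytosis (2d) and symptomatic or progressive splenomegaly (2b) are both on the list. Footnote 6 to Table 5.1 foresees patients with no measurable disease at baseline and waives their CT at cycles 12 and 24. Section 8.6 makes SD the category for anyone who meets neither PR nor definitive progression. Section 8.8 makes a time point non-evaluable when images are absent. Section 9.6 defines ORR as PR or CR, and section 2.2 lists duration of response among the secondary objectives.

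**The concern.** The two-criterion rule presumes that every patient has at least two parameters that were abnormal at baseline and can be followed. The exceptions relax it only for node-positive disease. A patient with no enlarged nodes and a single other abnormality cannot meet the rule from the data the protocol collects.

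Take a patient with lymphocytosis alone whose count falls from 120 to 2 x 10^9/L, whose blood counts normalise, and whose marrow still shows nodules. CR fails on the marrow. PR fails because only one criterion can be scored. The patient is recorded as stable disease.

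The misclassification follows the baseline pattern of disease, not the effect of treatment. It bears on ORR, on the response categories of section 9.5, and on who counts as a responder for duration of response.

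**Working it through.** **The plan's own figure.** Section 9.1 gives an exact 95% interval for 20% of 40 patients. With the Clopper-Pearson formula, lower limit = Beta quantile(0.025; x, n-x+1) and upper limit = Beta quantile(0.975; x+1, n-x). For x = 8 and n = 40 this gives 9.05% to 35.65%, width 26.6 points. The widest interval is at x = 20: 33.8% to 66.2%, width 32.4 points. Both match the plan. These are precision figures for the CR rate, and the PR rule does not enter them.

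**The response logic.** Each of nodes, lymphocytosis and liver/spleen enlargement that is present at baseline adds one scorable criterion. One criterion is needed for nodes alone or nodes with lymphocytosis, and two otherwise. The seven non-empty patterns are:

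| Baseline pattern | Needed | Scorable, no baseline marrow | PR reachable | Scorable, marrow at both times | PR reachable |
|---|---|---|---|---|---|
| Nodes only | 1 | 1 | yes | 2 | yes |
| Nodes + lymphocytosis | 1 | 2 | yes | 3 | yes |
| Nodes + liver/spleen | 2 | 2 | yes | 3 | yes |
| Lymphocytosis + liver/spleen | 2 | 2 | yes | 3 | yes |
| All three | 2 | 3 | yes | 4 | yes |
| Lymphocytosis only | 2 | 1 | **no** | 2 | yes |
| Liver/spleen only | 2 | 1 | **no** | 2 | yes |

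Two of the seven patterns are closed off on protocol-required data. The marrow columns show why: a marrow value at baseline and again on study would supply the second criterion, but the first is not scheduled and the second is taken only in radiographic CR. PR-L does not help, because it presupposes that the PR criteria are met.

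**Size per patient.** With 40 treated patients, one misclassified responder changes ORR by 1/40 = 2.5 points. The number affected, k, is not in the documents, so k is an assumption here. If all 40 would otherwise respond:

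| k | ORR = (40-k)/40 | Exact 95% CI |
|---|---|---|
| 0 | 100.0% | 91.2% to 100% |
| 1 | 97.5% | 86.8% to 99.9% |
| 2 | 95.0% | 83.1% to 99.4% |
| 4 | 90.0% | 76.3% to 97.2% |
| 6 | 85.0% | 70.2% to 94.3% |

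**The case against.** **A marrow may exist anyway.** Section 8 says all patients are evaluated with a bone marrow assessment, and footnote 5 lets FISH be done on marrow within 6 months of the first dose. A patient with a clinical pre-treatment marrow and an on-study marrow could score the criterion. This stands, so it would be wrong to infer that these patients can never be PR. The conclusion is limited to protocol-required data. Section 8 names no baseline time point and sits awkwardly with Table 5.1 and section 4.1, and reliance on chance records would make classification uneven.

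**The category may be NE, not SD.** Where footnote 6 waives the CT, section 8.8 read literally gives non-evaluable. This also stands, but the patient is a non-responder in ORR either way.

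**The endpoint is not central.** ORR appears as a definition in section 9.6 and is not among the objectives in section 2. Duration of response is an objective, but section 9.6 does not define it, so its restriction to responders is inferred. Both points limit the weight of the problem without removing it.

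**The cited guideline may settle it.** Sections 2.3 and 8 refer to published response criteria that are not part of the documents. Whether they cover single-parameter disease cannot be judged here. The protocol's own text does not cover it.

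**Conclusion.** The gap is real and moderate to minor. On protocol-required data, patients with lymphocytosis only, or liver or spleen enlargement only, who fall short of CR or CRi and have not progressed cannot be classed as PR. Each one who otherwise responds lowers ORR by 2.5 points at n = 40 and drops out of the responders. This rests on reading the blood-count and no-worsening conditions as additional to the two criteria, which their wording supports.

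Two stronger readings are tempting and not supported. A reader might infer an ORR loss of some 8 to 16 points. That needs 10% to 20% of patients to lack nodes and organ enlargement and 80% of those to miss CR (40 x 0.10 x 0.8 = 3.2 patients; 40 x 0.20 x 0.8 = 6.4). The documents give no such prevalence, and the 20% CR rate is anticipated for the whole trial, not this subgroup. A reader might also infer that ORR becomes incomparable with the 99.0% treatment-naive figure in section 1.4. That figure is background, no comparison with it is planned, and the PR rules behind it are not shown.

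The primary CR rate and its interval are unchanged by this rule.

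**What to change.** 1. Keep both exceptions in section 8.5 and add a third: *If only one of the listed parameters was abnormal at baseline and is assessable both at baseline and at the response assessment, only that parameter must improve to the extent specified.* Add it; do not substitute it for the existing two. Without the second exception, a patient with nodes and lymphocytosis would need both to improve, although sections 1.6 and 8.9 expect lymphocytosis on BTK inhibition.
2. Score the marrow criterion only where a pre-treatment and an on-study marrow are both on record. No new biopsy is needed. Bring the general statement on marrow assessment in section 8 into line with Table 5.1.
3. Reconcile footnote 6 with section 8.8, so that a CT waived because there was no measurable baseline disease does not by itself make the response NE. Without this, the change to 8.5 may not reach those patients. Section 8.8 should still apply to scans that were due and missed.
4. Show ORR by baseline disease pattern as well as overall.

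The cost is a few sentences of protocol text and one extra table. Stopping treatment for response depends on MRD-negative CR or CRi (section 4.3), so relabelling SD as PR does not trigger it. The small downside is that some PRs will rest on a single parameter, which item 4 makes visible.

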8.6 STABLE DISEASE

To satisfy criteria for SD, the following criteria must be met:

- No evidence of new disease
- There is neither sufficient evidence of tumor shrinkage to qualify for PR nor sufficient evidence of tumor growth to qualify for definitive PD

8.7 DEFINITIVE DISEASE PROGRESSION

The occurrence of any of the following events indicates definitive PD:

- Evidence of any new disease:
 - A new node that measures $> 1.5 \text{ cm}$ in the LD and $> 1.0 \text{ cm}$ in the LPD
 - New or recurrent splenomegaly, with a minimum LVD of 14 cm
 - New or recurrent hepatomegaly, with a minimum LVD of 20 cm
 - Unequivocal reappearance of an extra-nodal lesion that had resolved
 - A new unequivocal extra-nodal lesion of any size
 - *New non-target disease (e.g., effusions, ascites, or other organ abnormalities related to CLL).

*Isolated new effusions, ascites, or other organ abnormalities are not sufficient evidence alone of PD unless histologically confirmed. Thus, a declaration of PD should not be made if this is the only manifestation of apparently new disease.

- Evidence of worsening of target lesions, spleen or liver, or non-target disease:
 - Increase from the nadir by $\geq 50\%$ from the nadir in the SPD of target lesions
 - Increase from the nadir by $\geq 50\%$ in the LD of an individual node or extra-nodal mass that now has an LD of $> 1.5 \text{ cm}$ and an LPD of $> 1.0 \text{ cm}$

- Splenic progression, defined as an increase in splenic enlargement by $\geq 50\%$ from nadir (with a minimum 2 cm increase and a minimum LVD of 14 cm)
- Hepatic progression, defined as an increase in hepatic enlargement by $\geq 50\%$ from nadir (with a minimum 2 cm increase and minimum LVD of 20 cm)
- Unequivocal increase in the size of non-target disease (e.g., effusions, ascites, or other organ abnormalities related to CLL)
- Transformation to a more aggressive histology (e.g., Richter's syndrome) as established by biopsy (with the date of the biopsy being considered the date of CLL progression if the patient has no earlier objective documentation of CLL progression).
- Decrease in platelet count or hemoglobin that is attributable to CLL.
 - The current platelet count is $<100 \times 10^9/L$ OR there has been a decrease by $>50\%$ from the highest on-study platelet count.
 - The current hemoglobin is $<100 \text{ g/L (10.0 g/dL)}$ OR there has been a decrease by $>20 \text{ g/L (2 g/dL)}$ from the highest on-study hemoglobin.

If there is uncertainty regarding whether there is true progression, the patient should continue study treatment and remain under close observation pending confirmation of progression status by the IRC. In particular, worsening of constitutional symptoms in the absence of objective evidence of worsening CLL will not be considered definitive disease progression; in such patients, both CLL-related and non-CLL-related causes for the constitutional symptoms should be considered.

Worsening of disease during temporary interruption of study treatment (e.g., for inter current illness) is not necessarily indicative of resistance to study treatment. In these instances, CT/MRI or other relevant evaluations should be considered in order to document whether definitive disease progression has occurred. If subsequent evaluations suggest that the patient has experienced persistent definitive CLL progression, then the date of progression should be the time point at which progression was first objectively documented.

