8.2 IDENTIFICATION AND MEASUREMENT OF TUMOR LESIONS AND ORGANOMEGLALY

8.2.1 TARGET LESIONS

For patients with measurable adenopathy/disease at baseline, up to 6 lymph nodes should be selected as target lesions that will be used to quantitate the status of the disease during study treatment. Ideally, the target lesions should be located in disparate regions of the body. Only peripheral nodes need be selected as target lesions. However, it is optimal if mediastinal and retroperitoneal areas of disease are assessed whenever these sites are involved.

Target lesions will be measured and recorded at baseline and as per the study assessment schedule. The cross-sectional dimensions (the largest cross-sectional diameter, i.e., the LD x LPD) will be recorded (in cm) for each target lesion. The product of the perpendicular diameters (PPD) (in cm²) for each target

lesion and the sum of the products (SPD) (in cm^2) for all target lesions will be calculated and recorded. The baseline SPD will be used as references by which objective tumor response will be characterized during treatment. The nadir LD of individual lesions and the nadir SPD will be used as references by which CLL progression will be characterized. All LD and LPD diameters will be reported in centimeters and all PPDs and SPDs will be reported in centimeters squared.

A nodal mass may be selected as a nodal target lesion if it is both abnormal and measurable at baseline. A lymph node lesion is considered abnormal if it has a single diameter that is $> 1.5 \text{ cm}$ and is considered measurable if it has 2 perpendicular diameters that can be accurately measured in cross section with the LD being $\geq 1.0 \text{ cm}$ and the LPD also being $\geq 1.0 \text{ cm}$.

At follow-up time points, the LDs for individual lesions and the SPD of all nodal target lesions will be considered. Because nodal target lesions that have one or both diameters $> 0 \text{ cm}$ and $< 1.0 \text{ cm}$ cannot be reliably measured, a default value of 1.0 cm will be assigned for each diameter that meets these criteria and the resulting PPD will be used in SPD calculations. Based on this convention, a CR may be achieved even if an SPD value is $> 0 \text{ cm}^2$ (i.e., if all lymph nodes measure $< 1.0 \text{ cm}^2$).

A new node that measures $> 1.5 \text{ cm}$ in the LD and $> 1.0 \text{ cm}$ in the LPD will be considered progressive disease.

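### The summed-node (SPD) limb of definitive progression has no minimum node size, so a later scan on which every target node is normal can also be scored as progression

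*Combined protocol and SAP*

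**What the plan says.** Section 8.7 opens with "The occurrence of any of the following events indicates definitive PD", so one limb is enough. The limbs that rest on a measured size are:

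- **Summed nodes:** a rise of at least 50% "from the nadir in the SPD of target lesions". No minimum size and no minimum absolute increase is given.
- **Individual node:** a rise of at least 50% "in the LD of an individual node or extra-nodal mass that now has an LD of" more than 1.5 cm, with a perpendicular diameter (LPD) above 1.0 cm.
- **New node:** the same two limits, 1.5 cm and 1.0 cm.
- **Spleen:** "with a minimum 2 cm increase and a minimum LVD of 14 cm". The liver limb has a 2 cm increase and a 20 cm minimum.

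For complete response, 8.4 requires "Regression of all target nodal masses to normal size ≤ 1.5 cm in the LD". Section 8.2.1 makes the nadir SPD the reference for progression. For a diameter above 0 but below 1.0 cm, it says "a default value of 1.0 cm will be assigned for each diameter that meets these criteria". It adds in parentheses that CR remains possible with a non-zero SPD if all nodes are under 1.0 cm².

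The PR list in 8.5 excludes worsening that reaches the progression criteria. The CR list in 8.4 has no matching line.

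**The concern.** After a good nodal response the nadir nodes sit near 1 cm or at the default of 1.0 cm². A 50% rise from so small a reference can happen entirely within the range that 8.4 calls normal. The same measurements then support two opposite scores, and no text says which prevails.

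Progression is a PFS event under 9.6, and PFS and duration of response are secondary objectives (2.2). It is also a listed reason for leaving treatment (4.3) and fails the continuation criteria (7.2.2). A spurious progression would therefore add an event and could change what happens to the patient.

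**Working it through.** The plan gives no figure of its own on this point. Its one computed result, the exact interval for 8/40, reproduces (9.05% to 35.65%, width 26.6%; maximum width 32.4%), but nothing here depends on it.

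**Inputs.** Default diameter 1.0 cm and up to 6 target nodes (8.2.1); nodal CR limit LD ≤ 1.5 cm (8.4); SPD rise ≥ 50% from nadir (8.7).

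**Rule.** Product per node = LD x LPD, after setting each diameter above 0 and below 1.0 cm to 1.0 cm. SPD = sum of the products. The SPD limb is met if SPD now / nadir SPD − 1 ≥ 0.50. Nodal CR is met if every LD ≤ 1.5 cm.

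| Nadir | Later scan | SPD (cm²) | Change |
|---|---|---|---|
| 1 node at default | 1.3 x 1.2 cm | 1.00 to 1.56 | +56% |
| 6 nodes at default | six of 1.3 x 1.2 cm | 6.00 to 9.36 | +56% |
| 6 nodes of 1.1 x 1.0 cm | six of 1.4 x 1.2 cm | 6.60 to 10.08 | +53% |
| 6 nodes at default | six of 1.5 x 1.5 cm | 6.00 to 13.50 | +125% |
| 3 at default, 3 absent | six of 0.9 x 0.8 cm | 3.00 to 6.00 | +100% |
| 6 nodes at default | six of 1.5 x 0.6 cm (scored 1.5 x 1.0) | 6.00 to 9.00 | +50% |

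Every row meets the SPD limb and the 8.4 limit. None meets the individual-node limb, because no LD exceeds 1.5 cm. The third row does not use the default at all. The last two rows have true products of 0.72 and 0.90 cm², so they also satisfy the tighter parenthetical in 8.2.1.

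**When it can happen.** The largest product with a normal LD is 1.5 x 1.5 = 2.25 cm². A 50% rise that stays within it needs a mean nadir product of at most 2.25 / 1.5 = 1.5 cm² per target node.

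**When it cannot.** A target node at baseline must have LD > 1.5 cm and LPD ≥ 1.0 cm, so its product exceeds 1.5 cm². A 50% rise from there needs more than 2.25 cm², above the all-normal maximum. With baseline as nadir the overlap is impossible, so it needs a second post-baseline scan. Table 5.1 (footnote 6) schedules CT at the end of cycle 12, and at the end of cycle 24 only for those still on acalabrutinib. Other CTs are discretionary.

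**How often, from measurement error alone.** Assumed: unchanged nodes of true size 1.2 x 1.0 cm, independent error SD 0.10 to 0.25 cm, default applied, 400,000 simulated scan pairs per setting. Scans scored as progression with all nodes normal:

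- one target node: about 0.2% to 3.2%
- two: 0.5% or less
- three or more: under 0.1%

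If all 40 patients had one such scan pair, which overstates exposure, the expected false events would be 40 x 0.2% = 0.08 to 40 x 3.2% = 1.28 with one node each, at most 40 x 0.5% = 0.2 with two, and under 40 x 0.1% = 0.04 with three or more. One event is 1/40 = 2.5 percentage points.

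**The case against.** The best case against rests on reach. Patients in MRD-negative CR at cycle 12 stop therapy and have no scheduled CT afterwards. Those who continue have one scheduled opportunity, cycle 12 to cycle 24. The 3.2% figure needs a single target node and the largest assumed error, whereas 8.2.1 allows up to six targets. CR rate uses best overall response (8.3, 9.6), so a CR at cycle 12 survives a later progression. Section 8.7 also lets a patient continue while doubtful progression is confirmed by the IRC. All of this stands and limits the point.

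It does not remove it. The uncertainty clause is discretionary and sets no size limit, and a numerical criterion that has been met is not plainly uncertain.

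Three stronger readings are tempting but not supported:

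- **That patients in CR will be taken off treatment as progressors, with the best responders most exposed.** Only nodal CR is shown; full CR also needs marrow, blood counts, organ size and symptoms. The deepest responders are already off therapy, without scheduled scans.
- **That PFS is biased low by a known amount.** The documents give no frequency for the event. Change shared across nodes, such as reactive enlargement, would not average out as random error does, but nothing in the plan quantifies it.
- **That the PR rule in 8.5 needs loosening because the default caps shrinkage.** A 1.6 x 1.2 cm node (1.92 cm²) falling to the default shows only 1 − 1.0/1.92 = 48%. But that needs a lone target barely above abnormal, and 8.5 offers other routes outside two baseline patterns. Accepting any node of 1.5 cm or less would let 1.6 x 1.2 to 1.5 x 1.2 cm (1.92 to 1.80 cm², a 6% fall) count.

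**Conclusion.** The point holds in limited form. As written, 8.2.1, 8.4 and 8.7 allow one scan to be both nodal CR and definitive progression, and nothing in the text settles which score stands. The inconsistency follows from the rule constants alone and needs no assumption about data.

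Its reach is cycle 24 in patients continuing acalabrutinib, and discretionary CTs after a first post-baseline scan, where the mean nadir product is 1.5 cm² or less per target node. It affects PFS, the cycle 24 classification and duration of response, which 9.6 does not define and is taken here to end at progression. The CR rate is largely untouched; the exception is a patient who would first qualify for CR at cycle 24.

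The likely size from random error is small, at most about one event in 40 under the least favourable assumptions above. The frequency of correlated nodal change is unknown. This merits correction because the conflict is clear and cheap to remove, not because a large bias has been shown.

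**What to change.** Before PFS and duration of response are scored, the sponsor should reconcile four things: the SPD limb in 8.7, the nodal CR limit in 8.4, the default and the under-1.0 cm² parenthetical in 8.2.1, and the size limits in the neighbouring limbs of 8.7. The test of success is that no single scan can satisfy both nodal CR and progression. The settled rule should then be applied to all scans, including those already read. How it bears on stopping treatment (4.3, 7.2.2 and the uncertainty clause in 8.7) is for the sponsor to decide. Section 8.5 should be left as it is.

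The cost is a short clarification and no new data, since node diameters are already recorded. If the reconciliation makes the SPD limb harder to meet, some true early regrowth would be dated at a later assessment: up to 12 cycles later on the scheduled scans, and with no scheduled date after cycle 24.
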